# APPENDIX 2 ALS FUNCTIONAL RATING SCALE- REVISED (ALSFRS-R) (EXAMPLE)

1 Speech	6 Dressing and hygiene
4: Normal speech processes	4: Normal function
3: Detectable speech disturbance	3: Independent and complete self-care with effort or decreased efficiency
2: Intelligible with repeating	2: Intermittent assistance or substitute methods
1: Speech combined with nonvocal	1: Needs attendant for self-care
communication	
0: Loss of useful speech	0: Total dependence
2 Salivation	7 Turning in bed and adjusting bed clothes
4: Normal	4: Normal
3: Slight but definite excess of saliva in mouth; may have nighttime drooling	3: Somewhat slow and clumsy, but no help needed
2: Moderately excessive saliva; may have minimal drooling	2: Can turn alone or adjust sheets, but with great difficulty
1: Marked excess of saliva with some drooling	1: Can initiate, but not turn or adjust sheets alone
0: Marked drooling; requires constant tissue or handkerchief	0: Helpless
3 Swallowing	8 Walking
4: Normal eating habits	4: Normal
3: Early eating problems — occasional choking	3: Early ambulation difficulties
2: Dietary consistency changes	2: Walks with assistance
1: Needs supplemental tube feeding	1: Nonambulatory functional movement
0: NPO (exclusively parenteral or enteral feeding)	0: No purposeful leg movement
4 Handwriting	9 Climbing stairs
4: Normal	4: Normal
3: Slow or sloppy: all words are legible	3: Slow
2: Not all words are legible	2: Mild unsteadiness or fatigue
1: Able to grip pen but unable to write	1: Needs assistance
0: Unable to grip pen	0: Cannot do
5a Cutting food and handling utensils (subjects without gastrostomy)?	10 Dyspnea
4: Normal	4: None
3: Somewhat slow and clumsy, but no help needed	3: Occurs when walking
2: Can cut most foods, although clumsy and slow; some help needed	bathing, dressing (ADL)
1: Food must be cut by someone, but can still feed slowly	1: Occurs at rest, difficulty breathing when either sitting or lying
0: Needs to be fed	0: Significant difficulty, considering using mechanical respiratory support
5b Cutting food and handling utensils	11 Orthopnea

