#### Protocol MT-1186-A02

(alternate scale for subjects with gastrostomy)?	
4: Normal	4: None
3: Clumsy but able to perform all manipulations independently	3: Some difficulty sleeping at night due to shortness of breath, does not routinely use more than 2 pillows
2: Some help needed with closures and fasteners	2: Needs extra pillows in order to sleep (more than 2)
1: Provides minimal assistance to caregiver	1: Can only sleep sitting up
0: Unable to perform any aspect of task	0: Unable to sleep
	12 Respiratory insufficiency
	4: None
	3: Intermittent use of BiPAP
	2: Continuous use of BiPAP during the night
·	1: Continuous use of BiPAP during the night and day
	0: Invasive mechanical ventilation by intubation or tracheostomy

Abbreviations: ADL = activities of daily living; BiPAP = Bi-level Positive Airway Pressure

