3.3. Study Endpoints

3.3.1. Primary Endpoints

The primary efficacy endpoint is CAFS score at Week 48.

3.3.2. Key Secondary Efficacy Endpoints:

The following efficacy endpoints are defined as 'key' secondary and will be controlled for the familywise type I error:

- Change from baseline in % slow vital capacity (SVC) at Week 48
- Change from baseline in Amyotrophic Lateral Sclerosis Assessment Questionnaire (ALSAQ)40 at Week 48
- Time to death, tracheostomy or permanent assisted mechanical ventilation (\geq 23 hours/day)
- Time to death or permanent assisted mechanical ventilation (\geq 23 hours/day)
- Time to death

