8.4.2. Efficacy Measures

8.4.2.1. Combined Assessment of Function and Survival Score (CAFS)

CAFS ranks patients' clinical outcomes based on survival time and change in the ALSFRS-R score¹⁰.

CAFS Scoring:

To calculate a patient's CAFS, each patient is compared individually to all other patients in the study. The summary score for each patient is the sum of the comparisons (1, 0, 1) against all other patients (Figure 2). For each pairwise comparison of patients, the patient who fares better earns a point, and the one who fares worse loses a point. In the case of a tie, no points are added or subtracted. If both participants die, the one surviving longer fared better; if only one survives then that patient fared better; and if both participants survive, the one with the smaller decline in ALSFRS-R from baseline to week 48 fared better. If a participant discontinues early or ALSFRS-R at week 48 are missing, the participant will be treated as alive at week 48 and the ALSFRS-R at week 48 will be imputed missing using multiple imputation under missing mechanism assumption.

CAFS Ranking:

Next, patients' summary scores are ranked (Figure 3). In general, the ranking has the following characteristics:

- (1) The first patient who dies will have the lowest score and is ranked the lowest;
- (2) the last to die is ranked above all others who die;

- (3) Among survivors, the patient with the greatest decline in ALSFRS-R is ranked just above the last patient who died;
- (4) The surviving patients with the least decline in ALSFRS-R is ranked highest.

[REDACTED]

[REDACTED]

The average rank score is then calculated for each treatment group. A higher mean rank score indicates that participants in that treatment group, on average, fared better.

Figure 2: [REDACTED]

8.4.2.2. %Slow Vital Capacity (%SVC) Change from Baseline at week 4, 8, 12, 24, 36 and 48

SVC measurements will be conducted in clinic at around the same time of day where possible with the subject in sitting upright position. Subjects should make at least 3 attempts to generate acceptable and reproducible SVC data. If subjects cannot complete all three attempts due to disease progression or other reasons, it will not be considered a protocol deviation. The best value will be selected and will be recorded in the eCRF.

8.4.2.3. ALSAQ40 Change from Baseline at week 24 and 48

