- In case the event is not observed until the last observed visit date when week 48 data base is locked, a right censoring will be performed for each subject at the last observed date of treatment. the time variable for each subjects will be calculated as:
 - Last observed Date - Randomization date +1
- Indicator (censoring) variable will be created to indicate an event (0) if the event was observed or censoring (1) if the event is not observed and at week 48 data base lock the subjects was either discontinued or is ongoing.
-

8.4.2.5. Time to death or permanent assisted mechanical ventilation:

Variable derivation will be performed similar to the time to death, tracheostomy, or permanent assisted mechanical ventilation.

8.4.2.6. Time to death:

Variable derivation will be performed similar to the time to death, tracheostomy, or permanent assisted mechanical ventilation.

8.4.2.7. Changes from baseline in ALSFRS-R score at Weeks 4, 8, 12, 24, 36, and 48

ALSFRS-R is a questionnaire used to measure the impact of ALS that is evaluated by the Investigator. The scale measures the subjects' physical function across 12 activities of daily living. The date of the evaluation along with the results will be recoded on the eCRF with respect to "4 Handwriting" and "5 eating motion," the results for the dominant hand (the hand used in daily life at the time of screening) will be recorded.

- ALSFRS-R total score for each visit will be derived from the sum of 12 items²
For the item 5 “Eating disorder,” either the item (a) or (b) will be selected corresponding to subjects with or without gastrostomy respectively. The maximum total score is $4 \times 12 = 48$.
- ALSFRS-R domains Score. The following subdomain will be calculated for each visit as well as the change from baseline to week 48.
 - Bulbar function = total of items 1 to 3
 - Limb function = total of items 4 to 9
 - Fine motor function = total of items 4 to 6
 - Gross motor function = total of items 7 to 9
 - Respiratory function = total of items 10 to 12

8.4.2.7.1. Change from screening and baseline in %Forced Vital Capacity (%FVC) at Week 24 and 48

FVC measurements will be conducted in clinic at around the same time of day where possible with the subject in sitting upright position. Subjects should make at least 3 attempts to generate acceptable and reproducible FVC data. The best value will be selected and will be recorded in the eCRF.

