8.4.2.8. King's ALS Clinical Stage Derived from ALSFRS-R Score and Death Event

The King's ALS Clinical Staging System describes functional progression of ALS in terms of magnitude of disease involvement of different CNS regions (bulbar, upper limb, lower limb, need for gastrostomy and need for tracheostomy); according to its developers, the system was designed to inform patient-care decision making, resource allocation, research classifications, and clinical trial design11. Stages 1, 2, and 3 refer to the number of CNS regions (bulbar, upper limb, lower limb) involved at assessment, as described in Table 4 below. Stage 4A is defined solely by impairment of swallowing sufficient to require gastrostomy, and Stage 4B is defined solely by respiratory involvement sufficient to require ventilatory support. Functional involvement of three CNS regions is not a prerequisite to Stage 4A or 4B.

² Refer to Appendix I of the protocol.

Statistical Analysis Plan
Protocol No. MT-1186-A02

Mitsubishi Tanabe Pharma America, Inc.

While the King's ALS Clinical Staging System was designed initially for use as an assessment tool to be used in clinic, Balendra and colleagues¹² developed a method for estimating King's ALS Clinical Stages based on responses to ALSFRS-R items Q1 (speech), Q2 (salivation), Q3 (swallowing), Q4 (handwriting), Q5A/Q5B (self-feeding), Q8 (walking), Q10 (dyspnea), and Q12 (respiratory insufficiency)¹². The algorithm for mapping from responses to these items to King's Stage is also described in Table 4.

Table 4 : King's ALS Clinical Staging System

King's		Item Mapping
Stage	Definition	
1	Functional involvement of 1 CNS region	Bulbar involvement -- Score ≤ 3 on Q1, Q2, or Q3
2	Functional involvement of 2 CNS regions	Upper limb involvement -- Score ≤ 3 on Q4 or Q5A
3	Functional involvement of 3 CNS regions	Lower limb involvement -- Score ≤ 3 on Q8
4A	Need for gastrostomy	If Q5B is answered, rather than Q5A
4B	Need for non-invasive ventilation	Score of 0 on Q10 or score ≤ 3 on Q12
5	Death	

CNS: Central nervous system regions are bulbar, upper limb, and lower limb

Statistical Analysis Plan
Protocol No. MT-1186-A02

Mitsubishi Tanabe Pharma America, Inc.

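### SAP 8.4.2.7 reverses the rule for choosing ALSFRS-R item 5a or 5b, in the only visible derivation of the total score that feeds CAFS

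*SAP*

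**What the plan says.** SAP 8.4.2.7 defines the total: "ALSFRS-R total score for each visit will be derived from the sum of 12 items", with a maximum of 4 × 12 = 48. For item 5, which exists in two versions, it then says that "either the item (a) or (b) will be selected corresponding to subjects with or without gastrostomy respectively". The same section puts item 5 in the limb subscore (items 4 to 9) and the fine-motor subscore (items 4 to 6).

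The scale form in protocol Appendix 2 labels the first version "5a Cutting food and handling utensils (subjects without gastrostomy". The second is headed "5b Cutting food and handling utensils" and qualified as the "alternate scale for subjects with gastrostomy".

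SAP Table 4 (section 8.4.2.8) assigns King's stage 4A, need for gastrostomy, by the condition "If Q5B is answered, rather than Q5A".

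On the primary endpoint, SAP 3.3.1 states: "The primary efficacy endpoint is CAFS score at Week 48". SAP 8.4.2.1 compares pairs of subjects, and "if both participants survive, the one with the smaller decline in ALSFRS-R from baseline to week 48 fared better".

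**The concern.** The closing word of the SAP sentence makes the order of the two lists binding: the first version goes with the first group and the second with the second. That gives 5a to subjects with gastrostomy and 5b to subjects without, the opposite of the form that raters complete.

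This is an operative scoring rule, and two features of the SAP make the slip harder to catch. SAP section 2 says that its statistical detail takes precedence over the protocol's statistical description, so a programmer cannot simply assume that the protocol wins. The footnote to the total-score bullet sends the reader to protocol Appendix I, but protocol Appendix 1 contains the El Escorial diagnostic criteria. The ALSFRS-R form is in Appendix 2, so the reference that would expose the reversal leads to the wrong page.

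Gastrostomy is expected during the trial. Protocol 8.1 and 14.3 allow a switch to PEG/RIG dosing after baseline, and SAP 8.4.3.1 defines a PEG subgroup. Entry requires at least 2 points on every item (protocol 9.3, criterion 4) and the ability to take medication by mouth at baseline (protocol 9.4, criterion 16). Most subjects should therefore start on 5a, and some may move to 5b. The choice of version has to be right at both ends of a change from baseline.

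**Working it through.** The plan gives no figure to reproduce. The check sets the three statements side by side and then follows the rule through the possible ways of storing the data.

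**Step 1: the three statements.**

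| Source | Without gastrostomy | With gastrostomy |
|---|---|---|
| Protocol Appendix 2 (the scale) | 5a | 5b |
| SAP Table 4 (King's staging) | 5a (implied) | 5b |
| SAP 8.4.2.7 (total score) | 5b | 5a |

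The first two agree, and SAP 8.4.2.7 contradicts both. The sentence is complete and legible, so extraction or redaction does not explain it.

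**Step 2: where the rule reaches.** The total from 8.4.2.7 gives the change that ranks surviving pairs in CAFS (SAP 8.4.2.1), which is the primary endpoint (SAP 3.3.1). The total and its subdomains also go into the ALSFRS-R MMRM (SAP 9.2.1.5.1). Item 5 is in two subscores, limb and fine motor. Although 8.4.2.7 is headed as another secondary endpoint, it is the only total-score derivation that can be seen in the SAP.

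**Step 3: what happens under each storage assumption.** The documents do not say how the eCRF holds item 5, so each row is an assumption.

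| eCRF content per subject and visit | Programming | Item 5 obtained |
|---|---|---|
| Applicable version only | Takes whichever was answered | Correct, no effect |
| Applicable version only | Rule coded literally | Empty: looks for 5b where 5a was answered, and for 5a where 5b was answered |
| Both versions | Rule coded literally | Wrong version |

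In the second row item 5 is empty whether or not the subject has a gastrostomy. The total would then be missing too, unless a rule not visible in the SAP fills the gap.

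In the third row each version is scored 0 to 4, so the largest error at one visit is 4 − 0 = 4 points out of 48.

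**Step 4: what cannot be calculated.** The documents give neither the share of subjects with gastrostomy nor any sign that both versions are held. A net effect on the CAFS ranks or on the ALSFRS-R treatment difference cannot be derived.

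**The case against.** The strongest reply is that the rater's form fixes the version, not this sentence. The investigator completes the scale and enters it in the eCRF (protocol 12.1.1), and the form says which subjects each version is for. SAP 8.4.2.7 names no gastrostomy variable to drive a selection. Table 4 infers need for gastrostomy from which item was answered, so the authors evidently knew the right pairing. In practice a programmer would probably sum the answered item. Literal coding of single-version data would leave item 5 empty for everyone, which could hardly go unnoticed. All of this stands, and it is why the point is a small correction. It does not make the sentence right: a written derivation should not rely on the programmer disregarding it.

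Three stronger readings are tempting, and the documents support none of them.

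- A reader might infer that King's stage 4A is misclassified. Table 4 has its own item-level rule, which is correct and does not use the selection in 8.4.2.7.
- A reader might combine a missing total for every subject with an error of up to 4 points. These need different assumptions: the first that only one version is stored, the second that both are.
- A reader might call this the only scoring rule in the SAP. It is the only visible one. Parts of the CAFS section are redacted and little of the primary-analysis section can be seen.

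**Conclusion.** SAP 8.4.2.7 is wrong as written. It reverses the item 5 rule, against both protocol Appendix 2 and the SAP's own Table 4, and nothing visible in the documents corrects it. It matters because of where it sits: in the score behind the primary endpoint, the ALSFRS-R MMRM and two subscores.

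The likely practical effect is small. It is probably nil if the eCRF records only the applicable version and the answered item is used. It is a missing item 5 if that same data structure meets literal coding, and at most 4 of 48 points at a visit if both versions are held and the rule is followed. The quietest risk is the last, because a filled but wrong item would not show up as missing data.

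A reader might infer that the primary result is biased, or that the sponsor chose to score the scale this way. The documents show neither. No effect on the CAFS ranks is demonstrated, and the wording looks like a slip of word order. The point merits a correction before the analysis programs are finalised, and no more than that.

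**What to change.** In SAP 8.4.2.7, replace the selection sentence with: item 5a for subjects without gastrostomy and item 5b for subjects with gastrostomy. In the same bullet, rename item 5, now called an eating disorder, to match the form (cutting food and handling utensils). Change the footnote to cite protocol Appendix 2 instead of Appendix I. Then confirm that the analysis-dataset specification uses the corrected pairing.

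The cost is one sentence, two small text corrections and one check of the specification. No data collection, sample size or analysis model changes.

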8.4.2.8. King's ALS Clinical Stage Derived from ALSFRS-R Score and Death Event

The King's ALS Clinical Staging System describes functional progression of ALS in terms of magnitude of disease involvement of different CNS regions (bulbar, upper limb, lower limb, need for gastrostomy and need for tracheostomy); according to its developers, the system was designed to inform patient-care decision making, resource allocation, research classifications, and clinical trial design11. Stages 1, 2, and 3 refer to the number of CNS regions (bulbar, upper limb, lower limb) involved at assessment, as described in Table 4 below. Stage 4A is defined solely by impairment of swallowing sufficient to require gastrostomy, and Stage 4B is defined solely by respiratory involvement sufficient to require ventilatory support. Functional involvement of three CNS regions is not a prerequisite to Stage 4A or 4B.

² Refer to Appendix I of the protocol.

Statistical Analysis Plan
Protocol No. MT-1186-A02

Mitsubishi Tanabe Pharma America, Inc.

While the King's ALS Clinical Staging System was designed initially for use as an assessment tool to be used in clinic, Balendra and colleagues¹² developed a method for estimating King's ALS Clinical Stages based on responses to ALSFRS-R items Q1 (speech), Q2 (salivation), Q3 (swallowing), Q4 (handwriting), Q5A/Q5B (self-feeding), Q8 (walking), Q10 (dyspnea), and Q12 (respiratory insufficiency)¹². The algorithm for mapping from responses to these items to King's Stage is also described in Table 4.

Table 4 : King's ALS Clinical Staging System

King's		Item Mapping
Stage	Definition	
1	Functional involvement of 1 CNS region	Bulbar involvement -- Score ≤ 3 on Q1, Q2, or Q3
2	Functional involvement of 2 CNS regions	Upper limb involvement -- Score ≤ 3 on Q4 or Q5A
3	Functional involvement of 3 CNS regions	Lower limb involvement -- Score ≤ 3 on Q8
4A	Need for gastrostomy	If Q5B is answered, rather than Q5A
4B	Need for non-invasive ventilation	Score of 0 on Q10 or score ≤ 3 on Q12
5	Death	

CNS: Central nervous system regions are bulbar, upper limb, and lower limb

Statistical Analysis Plan
Protocol No. MT-1186-A02

Mitsubishi Tanabe Pharma America, Inc.

Since the MT-1186-A02 clinical trials will not collect information on King's Stage directly, ALSFRS-R item responses and patients' survival will be mapped to stages for every ALSFRS collected visit using the above published algorithm and patient-level data. Patients with baseline ALSFRS-R assessments that will not meet criteria for lower limb, upper limb, or bulbar involvement, and that also will not have evidence of Stage 4A or Stage 4B, will be designated "Stage 0", as their assessments could not be mapped to the King's ALS Clinical Staging System. For the King's stage derivation, the available ALSFRS-R data at each analysis visit will be used in the subjects who was not dead. If the subject was reported as a death from the last observation visit to last day of the nearest analysis visit window, King's stage from the analysis visit is Stage 5. If patients who was not death will have missing ALSFRS-R assessment at each visit, the last observation will be carried forward for the last King's stage value; In the vast majority of circumstances patients will either remain in the same clinical stage from one assessment to the next or they will experience a decline in stage. In those relatively rare instances, in which patients will be found to improve from one assessment to the next, the value from their immediately prior assessment will be used rather than the actual observed value, because the improvement will be considered to be temporary or spurious.

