## 9.3 Inclusion Criteria

Subjects who meet all the following criteria will be considered eligible to participate in the study:

- 1. Subjects or their LAR must provide a signed and dated informed consent form (ICF) to participate in the study. Subjects must be able (in the judgment of the Investigator) to understand the nature of the study and all risks involved with participation in the study. Subjects must be willing to cooperate and comply with all protocol restrictions and requirements.
- 2. Subjects will be male or female,  $\geq$  18 to 75 years of age at the time the ICF is signed.
- 3. Subjects will be diagnosed with Definite ALS or Probable ALS according to the El Escorial revised criteria (Appendix 1) for the diagnosis of ALS.
- 4. Subjects with a baseline score  $\geq 2$  points on each individual item of the ALSFRS- R at screening and baseline visits (Appendix 2).
- 5. Subjects have a screening and baseline %FVC  $\geq$  70%.
- 6. Subjects with 1- to 4-point decline for 8 weeks (±7 days) in ALSFRS-R total score between screening and baseline visits.
- 7. Subjects whose first symptom of ALS has occurred within 2 years of providing written informed consent.

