9.2.1.5.7. King's ALS Clinical Stage Derived from ALSFRS-R Score and Death Event

All analyses will be done using the FAS. A shift table to each visit up to week 48 from each baseline category will be summarized using number and percentages.

For the Kings ALS Clinical Staging System, attention will focus on two events of clinical

progression:

- Any decline in stage from baseline
- Any ≥ 2 -stage decline from baseline

These events will be analyzed in terms of both the proportion of patients who will experience the events between baseline and week 48 using chi square test for proportions, as well as the time to these events using stratified Log-rank test. For the latter, study dropouts prior to any event will be treated as censored as of the date of their first missing assessment. The time to event will be also displayed using the Kaplan Meier figure. Comparisons will be made between treatment groups on an overall basis, as well as controlling for stage at baseline.

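### A subject who enters in King's Stage 4B cannot have the 2-stage-or-more decline event, so that subject's death is a non-event in this one analysis (minor)

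*SAP*

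**What the plan says.** **Entry.** Protocol 9.3, inclusion criterion 4, asks for at least 2 "points on each individual item of the ALSFRS- R at screening and baseline visits". On item 12 (respiratory insufficiency) in Protocol Appendix 2, the scores below normal that this allows are "3: Intermittent use of BiPAP" and "2: Continuous use of BiPAP during the night". Protocol 9.4 has no exclusion for non-invasive ventilation.

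**Staging.** SAP 8.4.2.8 says that "Stage 4B is defined solely by respiratory involvement sufficient to require ventilatory support" and that "Functional involvement of three CNS regions is not a prerequisite to Stage 4A or 4B". Table 4 implements 4B as a score of 0 on Q10 or a "score ≤ 3 on Q12". Death is Stage 5. An apparent improvement is overwritten with the previous stage.

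**Analysis.** SAP 9.2.1.5.7 takes two progression events on the FAS. The first is any decline in stage. The second is any "2 -stage decline from baseline" or larger. Each is compared by a chi-square test on proportions and by a stratified log-rank test on time to event, both overall and controlling for baseline stage. For the log-rank test, "study dropouts prior to any event will be treated as censored as of the date of their first missing assessment". A shift table from baseline stage is also planned. SAP 9.2.1.5 adds that deaths after early discontinuation are included in the King's analysis.

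**The concern.** The second event needs room to fall by two stages. A subject already in 4B at baseline has only one stage left, so the event is impossible for that subject by definition. Section 9.2.1.5.7 makes no exception for death or for subjects near the top of the scale.

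Two things follow. First, a living Stage 1 entrant who reaches Stage 3 is an event, while a 4B entrant who dies is not. This sits awkwardly with the explicit inclusion of deaths in the King's analysis and with a plan that moved to CAFS because the death threshold was crossed. Second, 4B entrants stay in the denominator and the risk set as structural non-events, which shrinks the overall difference between arms.

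There is also a gap in the rules. The censoring sentence covers dropouts only. It does not say how to handle, or how to date, a death that fails the event definition.

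**Working it through.** The plan gives no sample size, event rate or power for King's stage, so there is no figure of its own to reproduce. The check is an enumeration, followed by illustrations on assumed values.

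**1. Can a subject enter in 4B?** Scores allowed at entry are 2, 3 and 4 on every item (Protocol 9.3). Table 4 gives 4B for Q10 = 0 or Q12 of 3 or less.
- Q10: 0 is not allowed at entry, so this route is closed.
- Q12: 2 and 3 are allowed, and both map to 4B.

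So the answer is yes, through Q12 only.

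**2. Largest possible decline.** This is the level of Stage 5 minus the level of the baseline stage. The SAP does not say whether 4A and 4B are one level or two, so both codings are shown.

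| Baseline stage | 4A and 4B tied | 4A, 4B, 5 as separate steps |
|---|---|---|
| 0 | 5 | 6 |
| 1 | 4 | 5 |
| 2 | 3 | 4 |
| 3 | 2 | 3 |
| 4A | 1 | 2 |
| 4B | 1 | 1 |

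From 4B the maximum is 1 under either coding. From 4A it is 1 only if the two are tied. Because improvements are overwritten, a 4B entrant cannot first move to a better stage and then fall two. The coding also matters elsewhere: a move from Stage 3 to 4B is one step if tied and two if separate.

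**3. How each planned analysis treats a 4B entrant who dies.**
- Any decline in stage: event, in both tests.
- Shift table: shown as 4B to 5.
- Decline of two or more, chi-square: non-event.
- Decline of two or more, log-rank: can only be a censored time. This follows from the event definition; it is not written, and no date is given.
- Decline of two or more, stratified by baseline stage: a 4B stratum has no events, so it adds zero to both observed-minus-expected and the variance. The dilution goes; the death is still not counted.

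**4. Size of the dilution (assumed values).** Let f be the 4B share, equal in both arms. Each arm's proportion is multiplied by (1 − f), and so is the difference. For an assumed 10-point difference: f = 3% gives 10 × 0.97 = 9.7 points; 5% gives 9.5; 10% gives 9.0. The ratio of proportions does not change.

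For power, assume event rates of 30% and 20% in the other subjects and 190 per arm. With d the difference in proportions and p̄ their mean, power = Φ[(d − 1.96·se0)/se1], where se0 = √(2p̄(1−p̄)/n) and se1 = √((p1(1−p1) + p2(1−p2))/n). Example at f = 10%: p1 = 0.27, p2 = 0.18, d = 0.09, se0 = 0.0428, se1 = 0.0426, so power = Φ(0.14) = 55.6%.

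| 4B share (assumed) | Rates in whole FAS | Power, all subjects kept | Power, 4B entrants excluded |
|---|---|---|---|
| 0% | 30.0% vs 20.0% | 61.5% | 61.5% |
| 3% | 29.1% vs 19.4% | 59.8% | 60.2% |
| 5% | 28.5% vs 19.0% | 58.6% | 59.3% |
| 10% | 27.0% vs 18.0% | 55.6% | 57.0% |

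Most of the loss comes from having fewer subjects who can have the event. Excluding the others recovers only about 0.4 to 1.4 points.

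**5. Deaths not counted (assumed values).** Deaths = 380 × f × mortality. At f = 3% and 5% mortality, 380 × 0.03 × 0.05 = 0.6. At f = 10% and 20% mortality, 380 × 0.10 × 0.20 = 7.6. Neither the shares nor a mortality rate for 4B entrants is in the documents.

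**The case against.** A ceiling is inherent in any measure of at least k steps on a bounded scale, and the plan has a companion event without this problem: any decline in stage counts 4B to 5 as progression. A reader might infer that the plan scores these deaths as no progression throughout. The documents do not support that; it is true of the 2-stage event alone. The same deaths also enter the CAFS primary analysis and the time-to-event key secondary endpoints.

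A reader might also infer that controlling for baseline stage is no remedy. For dilution that is wrong: if the control is by stratification, the empty 4B stratum drops out of the log-rank statistic. What remains is that the deaths are not recovered.

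Nor do the documents support a claim that the SAP prescribes informative censoring at death. The written rule names dropouts only, and within the 4B stratum the hazard of this event is zero, so censoring there loses no event.

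Finally, entry also requires %FVC of at least 70% and onset within two years, so 4B entrants may be few. Four-A entrants may be fewer still, since the swallowing item must be at least 2 at entry. The 7.6 deaths in the illustration need both assumed maxima at once, and the 19 deaths named in the plan are a threshold, not the observed count.

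All of this stands, and it limits the point. None of it supplies the missing rule: section 9.2.1.5.7 still gives an event that some eligible subjects cannot have even by dying.

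**Conclusion.** The gap is certain from the text and narrow in effect. Under the rules as written, a Stage 4B entrant cannot meet the 2-stage event, and a 4A entrant cannot if 4A and 4B are tied. The subject's death is then a non-event in the chi-square test and an undated censored time in the log-rank test. The structural non-events dilute the overall comparison; stratifying by baseline stage removes the dilution but not the miscounting of deaths.

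The size is unknown, because the documents do not give the 4B share, and it is probably small. On an assumed share of 3% to 10%, equal across arms, a 10-point difference loses 0.3 to 1.0 points. King's stage is an other secondary endpoint (SAP 3.3.3), outside hypotheses H01 to H06 (SAP 7.3), so no confirmatory conclusion depends on it. Severity: minor.

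**What to change.** In SAP 9.2.1.5.7, define the second event as a decline of two or more stages from baseline, or death at any baseline stage, dated at death in the log-rank test. State in SAP 8.4.2.8 whether 4A and 4B are one level or two. The added clause changes nothing for entrants in Stages 0 to 3, for whom death is already a fall of at least two.

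Alternatively, restrict this event to subjects whose baseline stage allows it, and report the others separately.

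The cost is one or two sentences and one line in the derivation, with no new data. The downside of the first option is that a one-step move to death counts as an event for 4B entrants (and for 4A entrants if tied). The downside of the second is that a few subjects leave this analysis.
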